6.1 Screening (Visit 1; Days -28 to -15)

Procedures as identified in Table 6-1.

- Written Informed Consent
- Medical and surgical history
- Prior medications
- Body weight and height
- Eligibility review
- Vital signs (blood pressure, heart rate, respiratory rate and body temperature)
- Physical examination (full)
- Chemistry, hematology (CBC) and urinalysis
- Serum C-reactive protein (CRP)
- Urine Pregnancy Test (women of childbearing potential only)
- Urine for protein and creatinine
- ECOG PS (see [Appendix C](#))
- Concomitant medications
- Dispense gastrointestinal AESI diary
- Dispense Bristol Stool Chart and diary
- Ferritin monitoring
- Trough PK sampling

6.2 Eligibility (Visit 2; Days -14 to -8)

Procedures as identified in Table 6-1.

- Washout Instructions
- Eligibility Review
- Serum CRP
- Review gastrointestinal AESI diary
- Review Bristol Stool Chart and diary
- Administer SICT questionnaire (see [Appendix D](#))
- Ferritin monitoring
- Pharmacogenetic monitoring

- Trough PK sampling (patients will be instructed not to take study medication before they arrive at the next visit)

Staff will discuss the randomization date for their randomization (Visit 3, Day 1) and ensure that the patient is aware of the 7-day washout period and procedure prior to Day 1.

6.3 Randomization and Period Treatment 1

6.3.1 Visit 3 (Day 1)

Procedures as identified in Table 6-1.

- Eligibility Review
- Randomization: subjects who were taking Exjade prior to study start will receive Exjade during the study and those taking Jadenu at study start will receive Jadenu.
- Dispense Investigational Product (see instructions in [Section 5.4](#))
- Vital signs (blood pressure, heart rate, respiratory rate and body temperature)
- Physical Examination (brief)
- 12-Lead electrocardiogram (ECG), predose/pre-sampling
- Chemistry, Hematology (CBC) and Urinalysis
- Serum CRP
- Urine for protein and creatinine
- ECOG PS (see [Appendix C](#))
- Adverse Events
- Concomitant Medications
- Collect gastrointestinal AESI diary and Bristol Stool Chart diary
- Review gastrointestinal AESI diary
- Review Bristol Stool Chart diary
- Dispense gastrointestinal AESI diary and Bristol Stool Chart and diary
- Treatment compliance
- Ferritin monitoring
- Pharmacokinetic sampling at predose (-0.5 hour) and 1, 2, 4, and 8 hours postdose
- Patients are instructed not to take study medication on the morning before they arrive for their next visit

6.3.2 Visit 4 (Day 7 ±1 day)

Procedures as identified in Table 6-1.

- Adverse Events
- Concomitant Medications
- Review GI AESI diary
- Review Bristol Stool Chart diary
- Treatment Compliance
- Pharmacokinetic sampling at predose (-0.5 hour) and 1, 2, 4, and 8 hours postdose
- Patients are instructed not to take study medication on the morning before they arrive for their next visit

6.3.3 Visit 5 (Day 14 ±1 day)

Procedures as identified in Table 6-1.

- Vital Signs (blood pressure, heart rate, respiratory rate and body temperature)
- Physical examination (brief)
- Chemistry, Hematology (CBC) and Urinalysis
- Urine for protein and creatinine
- Adverse Events
- Concomitant Medications
- Review GI AESI diary
- Review Bristol Stool Chart diary
- Treatment Compliance
- Patients are instructed not to take study medication on the morning before they arrive for their next visit

6.3.4 Visit 6 (Day 28 ±1 day)

Procedures as identified in Table 6-1.

- Provide washout instructions
- Vital signs (blood pressure, heart rate, respiratory rate and body temperature)
- Physical Examination (full)
- Chemistry, Hematology (CBC) and Urinalysis
- Serum CRP

- Urine for protein and creatinine
- ECOG PS (see [Appendix C](#))
- Adverse Events
- Concomitant Medications
- Collect gastrointestinal AESI diary
- Collect Bristol Stool Chart diary
- Review gastrointestinal AESI diary
- Review Bristol Stool Chart diary
- Treatment Compliance
- Ferritin monitoring
- Pharmacokinetic sampling at predose (-0.5 hour) and 1, 2, 4, and 8 hours postdose
- Patients are instructed not to take study medication on the morning before they arrive for their next visit

6.4 Period Treatment 2 (Crossover)

After a 7-day washout period the patients will attend the following visits for assessment of the second treatment.

6.4.1 Visit 7 (Day 36 ±1 day)

Procedures as identified in Table 6-1.

- Dispense Investigational Product (see instructions in [Section 5.4](#))
- Vital signs (blood pressure, heart rate, respiratory rate and body temperature)
- Physical Examination (brief)
- 12-Lead ECG (predose/pre-sampling)
- Chemistry, Hematology (CBC) and Urinalysis
- Serum CRP
- Urine for protein and creatinine
- ECOG PS (see [Appendix A](#))
- Adverse Events
- Concomitant Medications
- Dispense gastrointestinal AESI diary
- Dispense Bristol Stool Chart and diary
- Review gastrointestinal AESI diary

- Review Bristol Stool Chart diary
- Treatment Compliance
- Ferritin monitoring
- Pharmacokinetic sampling at predose (-0.5 hour) and 1, 2, 4, and 8 hours postdose
- Patients are instructed not to take study medication on the morning before they arrive for their next visit

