8.1 Sample Size Determination

The primary endpoints in this patient-pilot study are safety and tolerability with special interest in gastrointestinal AEs such as diarrhea. Evidence of DST-0509 iron chelating activity is also of special interest but is considered preliminary for this study and will not be considered in sample size estimations. If the underlying true probability of a diarrhea AE is 12% (Jadenu label 2015[2]), then there will be a 98% probability of observing at least one event in this study with a total sample size of 30 subjects. The table below presents a range of diarrhea AE rates provided from Jadenu clinical trials and the probability of observing at least 1 or 2 for our planned sample size. Given the same adverse event rate for diarrhea, there will be an 89% probability of observing at least two events in this study.

Underlying Event Rate	Probability of Observing at Least 1 Diarrhea AE		
	N=24	N=30	N=36
9%	0.90	0.94	0.97
12%	0.95	0.98	0.99
21%	>0.99	>0.99	>0.99

Underlying Event Rate	Probability of Observing at Least 2 Diarrhea Events		
	N=24	N=30	N=36
9%	0.65	0.77	0.85
12%	0.80	0.89	0.94
21%	0.97	0.99	>0.99

It is expected that most reasonably common AEs will be observed in this small study and will provide information for future studies.

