Dose reductions/interruptions of DST-0509 and Jadenu/Exjade are discouraged. However, in the event of a severe or higher AE lasting for >7 days, the PI, at their discretion, may reduce the dose by 25-33% or interrupt dosing. Max interruption is seven days. Dose re-escalation is not permitted. When AE resolves or is mild, the patient may restart study from last dose visit per PI or Medical Monitor (MM) discretion.

Dose suspension

Dosing with either treatment should be suspended in event of significant cytopenia – platelet count <50,000/ml or ANC <1,500/ml. If cytopenia has not recovered to Grade 1 or less after suspension of treatment for 7 days, the patient will be withdrawn from the study. The rationale for inclusion or exclusion of these subjects in the PK Population will be documented and listed.

Clinical Laboratory Parameters

Clinical laboratory measurements (serum chemistry, hematology and urinalysis) and changes from baseline will be summarized descriptively for each visit with the mean, median, standard deviation (SD), minimum and maximum, by treatment group.

Additionally, shifts from low, normal or high at baseline to low, normal or high at the end-of-treatment will be tabulated and presented by treatment group.

Vital Signs

Vital signs will be summarized descriptively for the mean, median, SD, minimum, and maximum by treatment group.

ECOG Performance Status

The ECOG performance status will be assessed at Screening Visit 1, and on Days 1, 28, 36 and 63. (see [Appendix C](#)). Changes from baseline will be presented with categorical descriptive statistics.

ECG Evaluation

ECG will be evaluated on Day 1 (Visit 3) and must be acquired predose and before blood samples are collected, and after a 5 min rest in supine position to avoid artifacts. Results will be provided in a patient listing.

Bristol Stool Chart Assessment

The Bristol Stool Chart (Section 7.13) will be used to evaluate average stool consistency: “What was the average stool consistency for the last 24 hours?” Stool Consistency will be presented with categorical description (N, % of patients) by visit for each consistency parameter: hard, lumpy, sausage, snake, soft, mushy or liquid. No formal inferential analysis will be conducted.

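### The GI and stool diaries are taken back on Day 28 and reissued only on Day 36, so the between-period washout has no diary record and the Day 36 diary review has nothing to review.

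*Protocol*

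**What the plan says.** Section 8.1 sets the weight of GI tolerability: "The primary endpoints in this patient-pilot study are safety and tolerability with special interest in gastrointestinal AEs such as diarrhea". Section 8.5.3 gives patients a diary in which to record GI AESIs throughout the study, and a Bristol Stool Chart with its own diary.

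Table 6-1 and Sections 6.1 to 6.4.4 fix when the booklets change hands. For Day 28, Section 6.3.4 lists "Collect gastrointestinal AESI diary" and the same for the Bristol diary, and dispenses neither. For Day 36, Section 6.4.1 lists "Dispense gastrointestinal AESI diary" and also "Review gastrointestinal AESI diary", with matching Bristol lines, and collects neither.

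On the stool chart, Section 8.5.3 asks for the average consistency over the last 24 hours and plans no inference. It adds: "Stool Consistency will be presented with categorical description (N, % of patients) by visit for each consistency parameter".

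**The concern.** The study is a two-period crossover in which GI tolerability is compared between products. The synopsis counts an event as treatment-emergent if it began, or became more severe, after dosing, and tabulates such events by treatment group. Applying that rule in Period 2 means knowing the patient's GI state in the days before the Day 36 dose. The diary is the prospective tool supplied for this, and it is missing for exactly those days.

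The two period baselines are therefore recorded differently: from a diary before Period 1, and from recall before Period 2. The difference runs with period, so in Sequence A it is the comparator that lacks a diary baseline and in Sequence B it is DST-0509. One-to-one allocation balances this across products. It does not stop a symptom left over from the first product being recorded as new or worsened on the second. A statistical analysis plan cannot restore data that were never collected.

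**Working it through.** **1. Who holds a diary, and when.** The table below is taken from Table 6-1 and the visit lists. The entries are the same for the GI AESI diary and the Bristol diary.

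| Visit (section) | Dispense | Collect | Review |
|---|---|---|---|
| Screening (6.1) | yes | no | no |
| Eligibility (6.2) | no | no | yes |
| Day 1 (6.3.1) | yes | yes | yes |
| Days 7, 14 (6.3.2, 6.3.3) | no | no | yes |
| Day 28 (6.3.4) | no | yes | yes |
| Day 36 (6.4.1) | yes | no | yes |
| Days 42, 49 (6.4.2, 6.4.3) | no | no | yes |
| Day 63 (6.4.4) | no | yes | yes |

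Each diary is dispensed three times and collected three times, and these pair off: Screening to Day 1, Day 1 to Day 28, and Day 36 to Day 63. No booklet is with the patient between Day 28 and Day 36. On Day 1 the full set of collect, review and dispense is listed. On Day 36 the collect step is absent because nothing was issued on Day 28.

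**2. Washout coverage.**

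- Before Period 1 (Days -7 to -1), the Screening diary is in use until Day 1: 7 of 7 days.
- Before Period 2 (Days 29 to 35): 0 of 7 days.
- With diaries dispensed on Day 28: 7 of 7 days.

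**3. Sample-size figures.** Section 8.1 takes a diarrhea rate of 12% and N = 30, and says "there will be a 98% probability of observing at least one event in this study with a total sample size of 30 subjects" and "there will be an 89% probability of observing at least two events in this study".

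- P(at least 1) = 1 - 0.88^30 = 1 - 0.0216 = 0.978 (stated 0.98).
- P(at least 2) = 1 - 0.0216 - 30 × 0.12 × 0.88^29 = 1 - 0.0216 - 0.0884 = 0.890 (stated 0.89).

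All 18 cells of the two tables in that section reproduce. They count patients with a diarrhea adverse event, not diary or stool scores, so the diary gap does not alter them.

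**4. The Bristol table (secondary).** The on-treatment visits are Days 7, 14 and 28 in Period 1 and Days 42, 49 and 63 in Period 2. The protocol does not say whether the 24-hour question is answered daily or once per visit. If once per visit, the table covers 3/28 = 10.7% of treatment days in each period. If every diary day is summarised, it covers 28 of 28.

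**The case against.** The strongest reply is that adverse events do not depend on the diary. Under Section 8.5.3 they are captured from the first dose to Visit 11 or early termination, which includes the washout. Under Section 9.2 patients are questioned at every visit, and each event is entered with dates and severity. A symptom that persists from Period 1 or starts in the washout should therefore carry an onset date before the Day 36 dose. The protocol defines no change from baseline in diary scores, so no stated analysis breaks. This stands, and it makes the gap a partial loss. What remains is that on Day 36 the patient must recall a week without the tool that recorded the corresponding week before Period 1.

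The Day 36 review might be read as a second look at the Period 1 diary. That diary was already reviewed and collected on Day 28, and this reading still leaves Days 29 to 35 unrecorded.

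A reader might also infer that GI tolerability is summarised only over 24-hour windows and that most diarrhea is missed. The protocol does not support this. The 24-hour question belongs to the Bristol chart alone. The GI AESI diary has no such window and is held through both treatment periods, and diarrhea is also captured as an adverse event. For the Bristol table by itself, the share of episodes missed depends on two things the protocol does not give: one rating per visit, and episode length. With uniform onset it runs from 89% for 1-day episodes through 46% for 5-day episodes to 25-29% for 7-day episodes. That describes one descriptive table, not the capture of diarrhea.

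**Conclusion.** The schedule contradicts itself: Day 36 calls for review of diaries that no patient holds. As a result, diary coverage of the washout is 0 of 7 days before Period 2, against 7 of 7 before Period 1. This rests only on the dispensing and collection entries, which agree between Table 6-1 and the visit lists. The consequence is that the diary cannot classify GI symptoms at the start of Period 2 as residual, new or worsened. Adverse event enquiry reduces the harm but does not remove it, and the protocol gives no basis for saying how many events would be misattributed. The stated 98% and 89% stand.

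The Bristol point is minor. The figure of 3 in 28 days holds only if stool is rated once per visit, and the table is descriptive support, not the basis of the tolerability comparison.

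**What to change.** - In Table 6-1 and Section 6.3.4, dispense a new GI AESI diary and a new Bristol diary at Visit 6 (Day 28).
- In Table 6-1 and Section 6.4.1, add collection of both at Visit 7 (Day 36). The review already listed there then has a diary to work from.
- State that the washout week before each period (Days -7 to -1 and Days 29 to 35) is that period's diary baseline.
- As a secondary change in Section 8.5.3, add to the by-visit Bristol table a summary per period and by treatment from all diary days. It should give the number of days with mushy or liquid stool and with hard or lumpy stool, and the number and percentage of patients with any such day.

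The cost is one more booklet of each diary per patient, one more week of diary completion, and an added table. No visit or procedure is added.

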6.4.2 Visit 8 (Day 42 ±1 day)

Procedures as identified in Table 6-1.

- Adverse Events
- Concomitant Medications
- Review gastrointestinal AESI diary
- Review Bristol Stool Chart diary
- Treatment Compliance
- Pharmacokinetic sampling at predose (-0.5 hour) and 1, 2, 4, and 8 hours postdose
- Patients are instructed not to take study medication on the morning before they arrive for their next visit

6.4.3 Visit 9 (Day 49 ±1 day)

Procedures as identified in Table 6-1.

- Vital Signs (blood pressure, heart rate, respiratory rate and body temperature)
- Physical examination (brief)
- Chemistry, Hematology (CBC) and Urinalysis
- Urine for protein and creatinine
- Adverse Events
- Concomitant Medications
- Review gastrointestinal AESI diary
- Review Bristol Stool Chart diary
- Treatment Compliance
- Patients are instructed not to take study medication on the morning before they arrive for their next visit

6.4.4 Visit 10 (Day 63 ±1 day)/Early Termination (ET)

Procedures as identified in Table 6.1.

- Washout Instructions
- Vital signs (blood pressure, heart rate, respiratory rate and body temperature)
- Physical Examination (full)
- Chemistry, Hematology (CBC) and Urinalysis
- Serum CRP
- Urine for protein and creatinine
- ECOG PS (see [Appendix C](#))
- Adverse Events
- Concomitant Medications
- Collect gastrointestinal AESI diary
- Collect Bristol Stool Chart diary
- Review gastrointestinal AESI diary
- Review Bristol Stool Chart diary
- Treatment Compliance
- Ferritin monitoring
- Pharmacokinetic sampling at predose (-0.5 hour) and 1, 2, 4, and 8 hours postdose (not performed for ET)

6.5 Follow-up (Phone Call; Day 70 ±1 day)

Patients will be called 7 days after the last dose of investigational product to assess if they have undergone the 7-day washout period, before recommencing iron chelation treatment with their prior therapy, and they will be asked if there were any new or ongoing adverse events or concomitant medication use.

6.6 Early Termination Procedures

The term "Early Termination" refers to a patient's non-completion of a study whether by his or her own choice or the Investigator's decision or due to discontinuation of the study by DisperSol.

In the absence of a medical contraindication or significant protocol violation, every effort will be made by the Investigator to keep the patient in the study. Should the patient decide to

withdraw, an attempt will be made to conduct an early termination visit, which will include all procedures normally done at Visit 10 (Day 63) and, the patient should be requested to undergo a 7-day washout and have a phone call to confirm as in the Follow-up (Day 70) procedures.

The primary reason for a patient withdrawing prematurely should be selected from the following categories:

Adverse Event or Serious Adverse Event - events that are associated with discontinuation.

Noncompliance with protocol - The patient failed to adhere to the protocol requirements. The deviation necessitated premature termination from the study.

Pregnancy - The patient became pregnant after enrolling the study. Pregnant patients are withdrawn from the study as soon as the Principal Investigator is aware of the condition.

Laboratory Abnormality - Laboratory abnormality that does not meet the definition of an AE.

Withdrawal of Consent - The patient desires to withdraw from further participation in the study in the absence of an adverse event or a medical need to withdraw.

Lost to Follow-up - The patient did not return for follow-up visit(s) following dispensing of test drug.

Other - causes of premature termination from the study other than the above, such as theft or loss of investigational product, termination of study by DisperSol, etc.

The Investigator should notify Accelovance, Inc. promptly when a patient is withdrawn, or if the study is stopped at his/her site by the IRB or if the Investigator elects to stop the study.

6.7 Patient Completion Criteria

For purposes of this study, patients who have not discontinued investigational product early will be defined as study completers; interruption/missed dosing will be discussed with the PI. If the subject does not have the Follow-up (Day 70) phone to confirm washout, the subject will still be considered a completer.

6.8 Protocol Deviations

This study is intended to be conducted as described in this protocol. In the event of a significant deviation from the protocol due to an emergency, accident, or mistake, the Investigator or designee will document the deviation. The protocol deviations will be reviewed by the Medical Monitor throughout the study.

7 DETAILED DESCRIPTION OF ASSESSMENTS

7.1 Informed Consent

Written IC will be obtained from each patient before any study procedures are performed. All potentially eligible patients for the study will be given a copy of the Institutional Review Board (IRB)-approved informed consent form to read.

The protocol will be discussed in detail with each potentially eligible patient. The PI or qualified designee will explain all aspects of the study in lay language and answer all the patient's questions regarding the study. The PI will inform the patient as to the nature, aims, duration, potential hazards, and procedures to be performed during the study and that his/her medical records may be reviewed. The PI will also explain that the patient is completely free to refuse to enter the study or to withdraw from it at any time. Patients who refuse to participate or who withdraw from the study will be treated without prejudice.

The study patient must sign the IC form if he/she decides to participate in the study. No study procedures will be performed, and investigational products will not be released to any patient who has not signed the IC form.

7.2 Medical History

A complete medical and surgical history will be obtained at Screening (Visit 1).

7.3 Prior Medications and Concomitant Medications

Any therapy taken within 30 days of Visit 3 (Day 1) by the patient will be reported as prior medication. Any therapy started or stopped by the patient during the study after randomization will be regarded as concomitant therapy.

All prior and concomitant medications (prescription and over the counter, vitamins, and mineral supplements, and/or herbs) will be documented and must include the following information:

- Medication name
- Indication
- Dose
- Route of administration
- Start date

- Stop date or “Ongoing”

7.4 Prohibited Medications

Glucuronidation is the main metabolic pathway for DFX, with subsequent biliary excretion. Deconjugation of glucuronides in the intestine and subsequent reabsorption (enterohepatic recycling) is likely to occur [1, 2].

DFX is mainly glucuronidated by UGT1A1 and to a lesser extent UGT1A3. The concomitant use of DFX with potent uridine diphosphate glucuronosyltransferase (UGT) inducers (e.g., rifampicin, phenytoin, phenobarbital, ritonavir) is prohibited, as these compounds may result in a decrease in DFX efficacy due to a possible decrease in DFX concentration. CYP450-catalyzed (oxidative) metabolism of DFX appears to be minor in humans (about 8%). Deconjugation of glucuronide metabolites in the intestine and subsequent reabsorption (enterohepatic recycling) was confirmed in a healthy volunteer study in which the administration of cholestyramine 12 g twice daily (strongly binds to DFX and its conjugates) 4 and 10 hours after a single dose of DFX resulted in a 45% decrease in DFX exposure (AUC) by interfering with the enterohepatic recycling of DFX [1, 2].

The concomitant use of DFX with bile acid sequestrants is prohibited, as these agents may result in a decrease in DFX efficacy. In healthy volunteers, the administration of cholestyramine after a single dose of DFX resulted in a 45% decrease in DFX exposure (AUC). Although DFX has a lower affinity for aluminum than for iron, avoid use of DFX with aluminum-containing antacid preparations due to the mechanism of action of DFX [1, 2].

If a patient begins taking a prohibited medication, the Medical Monitor should be notified of the deviation for approval to continue in the study. Notable prohibited medications include, for example, repaglinide, theophylline and midazolam.

